1.2 Pharmacokinetics

FN-1501 showed wide distribution volume and fast plasma clearance (CL) in in vivo studies. In plasma protein binding assays using mouse, rat, dog, monkey, and

August 21, 2019 Confidential 26 / 74

human plasma, FN-1501 exhibited a moderate binding (\geq 50% and <95.0%) to plasma proteins in all 5 species within the range of 0.2 μ M to 10 μ M. No drug accumulation was observed after 7-day consecutive intravenous injection at 3.64 mg/kg/day in rats or at 0.456 mg/kg in monkeys.

After single intravenous slow injection at 1.21, 3.64, and 7.28 mg/kg to Sprague-Dawley rats, FN-1501 showed the maximum observed plasma concentration (C_{max}) values of 197 ± 70.7 , 580 ± 42.8 , and 1510 ± 291 ng/mL, respectively, and plasma CL of 117 ± 17.1 , 139 ± 19.6 , and 98.5 ± 11.0 mL/min/kg, respectively. Apparent volume of distribution at steady state (Vdss) was 22.0 ± 7.51 , 21.9 ± 1.84 , and 17.8 ± 4.01 L/kg, respectively, and terminal half-life ($t_{1/2}$) was 2.82 ± 0.749 , 2.51 ± 0.0817 , and 3.01 ± 0.469 hours, respectively. Following single intravenous slow injection administration of FN-1501 at 0.152, 0.456, and 0.912 mg/kg in cynomolgus monkeys, C_{max} appeared immediately after infusion. The C_{max} values were 263 ± 62.2 , 780 ± 51.4 , and 1480 ± 164 ng/mL, respectively; CL was 42.3 ± 5.40 , 34.8 ± 5.68 , and 28.4 ± 4.04 mL/min/kg, respectively; the Vdss was 5.88 ± 1.20 , 8.58 ± 1.60 , and 9.18 ± 1.91 L/kg, respectively; $t_{1/2}$ was 2.40 ± 0.286 , 4.56 ± 1.88 , and 6.77 ± 1.96 h, respectively.

After single intravenous slow injection at 3.64 mg/kg to Sprague-Dawley rats, FN-1501 distributed to all tissues within 15 minutes. The highest tissue exposure area under plasma concentration-time curve (AUC)_{0-last} was observed in spleen.

A total of 8 drug metabolites were identified in liver microsomes of mouse, rat, dog, monkey, and humans after incubation with FN-1501 at 37°C for 60 minutes. The four metabolites detected in human liver microsomes were all found in monkey liver microsomes, suggesting that no unique metabolites were formed in human liver microsomes. Among the four metabolites detected in human liver microsomes, three (M4, M5, M7) were in low level while M3 was 16.89% of total drug. FN-1501 was mainly metabolized via oxidation and N-demethylation. cytochrome P450 (CYP)3A was the major metabolic enzyme; other CYP isozymes played minor or no role in the metabolism of FN-1501.

FN-1501 was mainly excreted through feces and urine. Following single intravenous slow injection of FN-1501 at 3.64 mg/kg to male and female Sprague-Dawley rats, the gender averaged drug recovery of FN-1501 from feces and urine at 120 hours post dose was $54.4 \pm 9.55\%$ of nominal dose, and feces was the main excretion pathway. The gender averaged drug recovery of FN-1501 from bile at 72 hours post dose was $18.2 \pm 5.55\%$ of nominal dose.

Please refer to the IB for more detailed information on the PK of FN-1501 [4].

August 21, 2019 Confidential 27 / 74

1.3 Toxicology

The non-clinical toxicity profile of FN-1501 was characterized in both rats and monkeys in single and repeat dose studies up to 28 days, and in a core battery of genotoxicity tests, including in vitro Ames and chromosomal aberration assays, and an in vivo bone marrow micronucleus assay in mice.

FN-1501 related pathological changes in rats include weakness, eye discharge, squint, reduced spontaneous motor activities, reduced body weight and body weight gain, lacrimation, sparse hair, macropathological ulcer and swelling on skin, decreased blood cell count and histological ulcer and swelling of dermatitis. Possible test article-related pathological changes were osteosclerosis in bone marrow (femur and sternum), basophilic tubule in kidney, and atrophy in thymus. The maximum tolerated dose (MTD) was 15 mg/kg in a repeated-dose toxicity study and the lethal dose was 40 mg/kg in an acute toxicity study in rats.

FN-1501 related pathological changes in monkeys included erythema and edema at injection sites, foot ulcer, and decreased blood cell count. Possible test article-related pathological changes were small thymus, thymus atrophy, and necrosis. The MTD of FN-1501 in monkeys was 10 mg/kg in an acute toxicity study and 2 mg/kg in a 28-day repeated-dose study.

The study on human ether-a-go-go-related (hERG) current showed that FN-1501 inhibited hERG current of HEK-293 cells, wherein 50% inhibition concentration (IC₅₀) was $2.870 \mu M$.

FN-1501 transiently and mildly elevated diastolic blood pressure (DBP) and mean arterial blood pressure at the dosage of 2 and 4 mg/kg and decreased body temperature at the dosage of 4 mg/kg. There were no effects on electrocardiogram (ECG) parameters at any dose level in this study.

No mutagenicity or genotoxicity was detected in the absence and presence of a metabolic activation system.

Refer to the IB for more detailed information on the toxicity of FN-1501 [4].

1.4 Rationale in Acute Myeloid Leukemia

AML accounts for about 80% of adult acute leukemia cases, with an incidence of 3-5/100,000 in the United States (US). The incidence of AML increases with age. For example, the incidence of AML increases from 1.3/100,000 in those under 65 to 12.2/100,000 in those 65 and above. The "3+7" induction chemotherapy, i.e., 1-2 cycles of the standard-dose of cytarabine (Ara-c) in combination with anthracyclines (rubidomycin, daunorubicin, etc.) is the recommended first line treatment for AML, which exhibits a complete remission rate of higher than 80%, then followed by the

August 21, 2019 Confidential 28 / 74

consolidation chemotherapy (1-3 cycles of Ara-c). The 5-year overall survival (OS) can reach 40-50% with this regimen. However, after being treated with the "3+7" treatment scheme for 1-2 cycles, 10% to 40% of patients with AML fail to achieve complete response (CR) or relapse within six months after the first CR. No drug has yet been approved by the Food and Drug Administration (FDA) in treatment of recurrent/refractory AML and clinical trials are strongly recommended. Currently, the only treatment option is incremental dose of Ara-c or combination of multiple drugs, which bear non-significant efficacy in terms of remission rate and long-term OS benefit.

AML is caused by abnormal proliferation and differentiation of hematopoietic stem cells (HSC), characterized by clinical manifestations and significant biological heterogeneity. Nearly all (97%) of AML patients present molecular abnormality to a certain degree, FLT3 mutations are found in 30% of them [5]. FLT3 belongs to the Type III RTK family. FLT3 consists of four domains: 1) extracellular N-terminus including 5 immunoglobulin-like domains, is a ligand-binding site; 2) transmembrane domain; 3) intracellular juxtamembrane domain (JM) and 4) intracellular C--terminal kinase domain. When ligands bind to extracellular region, FLT3 receptors are dimerized, terminal kinase domain is activated to release the intracellular signaling molecules, and the growth and development of HSC are regulated through PI3K/AKT and MAPK signaling pathways. FLT3/ITD mutation is the most common FLT3 mutation, which accounts for about 20% of all FLT3 mutations. ITD mutation leads to non-ligand-dependent dimerization of FLT3, continuously activates intracellular signaling pathways, realizes non-cytokines-dependent cell proliferation and differentiation disorders thus results in leukemia. FLT3 point mutation can be found in 7%-10% AML patients, and its correlation with AML is not fully understood. At present, development of FLT3-ITD-targeted therapeutics is very active and FDA granted Breakthrough Therapy designation to Midostaurin in February 2016 and Priority Review status was granted in November 2016. In 2017, Midostaurin became the first potential AML targeted therapy approved by FDA. In their pivotal trial, midostaurin plus standard chemotherapy was superior to placebo plus standard chemotherapy in OS (HR 0.77; 95% CI 0.63, 0.95; 2 sided p = 0.016) [6].

FN-1501, a new investigational inhibitor of FLT3, may provide clinical benefit for patients in the treatment of relapsed or refractory AML with or without the presence of the FLT3 mutation.

1.4.1 Rational for Starting Dose Selection

A dose of 2.5 mg/day is selected as the starting dose in this study based on the International Council for Harmonisation of Technical Requirements for Pharmaceuticals for Human Use (ICH) S9 [7] and results of toxicological studies. ICH S9 recommends that the starting dose should be 1/6th of MTD observed in non-

August 21, 2019 Confidential 29 / 74

rodent studies. The MTD is calculated as 2 mg/kg from the 28-day repeated intravenous infusion toxicity study in monkeys. Using the conversion factors published in the FDA Guidance for Industry, *Estimating the Maximum Safe Starting Dose in Initial Clinical Trials for Therapeutics in Adult Healthy Volunteers* (2005) [8], the human equivalent dose (HED) derived from 1/6th of the monkey MTD is 6.48 mg/d. However, considering FN-1501 as a novel API with limited toxicity data, we set the lower starting dose at 1/10th of MTD calculated from the 28-days repeated toxicity study in monkeys, which is 3.88 mg/d. Because the strength of FN-1501 is 10 mg/vial and 3.88 mg/d is not convenient in clinical practice, we finally choose 2.5 mg (1/4 × 10 mg) as the safe starting dose for the First-in-Human clinical trial.

2 Study Objectives

2.1 Primary Objectives

To evaluate the safety and tolerability of FN-1501

To determine the MTD and recommended phase 2 dose (RP2D)

2.2 Secondary Objectives

To characterize the PK of FN-1501 and major metabolites

To describe the preliminary anti-tumor activity of FN-1501

3 Study Endpoints

3.1 Primary Endpoints

The safety of FN-1501 will be assessed throughout the study by monitoring adverse events (AEs) and serious adverse events (SAEs) [per the National Cancer Institute-Common Terminology Criteria for Adverse Events (NCI-CTCAE) Version 4.3], physical examination, and laboratory measurements.

The MTD of FN-1501 will be the highest dose under which one or no case of dose limiting toxicity (DLT) is observed while the RP2D of FN-1501 will be determined based on PKs, safety and tolerability, as well as preliminary efficacy.

3.2 Secondary Endpoints

Blood sample collection:

Cycle 1 Day 1: pre-dose, post dose 5, 15, 30 minutes, 1, 2, 4, 6, 8, 12, 24, and 48 hours and on Day 8 prior to that days dose (if applicable)

PK for single dose profile:

August 21, 2019 Confidential 30 / 74

AUC from zero to the last measurable concentration (AUC_{0-last}), AUC from 0 to 24 hours (AUC₀₋₂₄), AUC from zero to infinity (AUC_{0- ∞}), C_{max}, time to maximum observed plasma concentration (t_{max}), t_{1/2}, CL, apparent volume of distribution (Vd), and Linear Index (LI).

Endpoints for anti-tumor activity evaluation

Anti-tumor activity will be evaluated by investigators according to Response Evaluation Criteria in Solid Tumors (RECIST) v1.1 (solid tumor), performance status, and Computed Tomography (CT)/ Magnetic Resonance Imaging (MRI) image at designated time point and time of event. Imaging for disease assessment will be performed every 6 weeks to summarize CR, partial response (PR), stable disease (SD), progression-free survival (PFS), and duration of response for patients with solid tumors.

In patients with AML, response will be evaluated according to the AML response criteria [5]. Bone marrow assessments will be performed at Screening, the end of every other cycle, and at the end of the study or at time of relapse.

Based on the patient's clinical condition, complete blood counts or bone marrow assessments may occur more frequently based on Investigator's judgment.

4 Investigational Plan

4.1 Summary of Study Design

This is a phase 1, first-in-human, open-label, multi-center, single-arm, dose escalation clinical study in patients with histologically or cytologically confirmed advanced solid tumors or relapsed/refractory AML, who cannot tolerate or do not respond to standard systemic therapy.

Patients will be screened for eligibility for up to 21 days prior to entry into the study. The starting dose will be 2.5 mg/day on the assigned days. Dose escalation will use the traditional 3+3 design and follow a modified Fibonacci sequence until MTD is reached. Increments of 33% in the dose of FN-1501 will be undertaken after reaching 30 mg/day. Eligible patients will receive a single intravenous infusion of study drug on Days 1, 3, 5, 8, 10, and 12 of a 21-day cycle.

The DLT assessment period is 21 days from the first dose of FN-1501. Evaluation of a cohort of at least three (3) patients completing DLT assessment at any given dose level is required prior to determining the next dose level and dose regimen for the subsequent cohort.

August 21, 2019 Confidential 31 / 74

The highest dose under which one or no case of DLT is observed will be considered as MTD. If DLT cannot be observed, RP2D will be determined based on safety, preliminary anti-tumor activities and PK data.

Approximately thirty-three patients are expected to be enrolled.

After the first patient in the cohort receives the Cycle 1, Day 1 dose, subsequent patients in that cohort will not be dosed until the first patient has been evaluated for at least 48 hours to exclude unexpected acute toxicity. The continuous safety evaluation will be performed by investigators, the medical monitor, and the sponsor. A Safety Monitoring Committee (SMC) will determine dose levels to be administered and dose regimen during dose escalation based on the data available from the previous dose levels. If an MTD is not identified due to paucity of DLTs, the RP2D will be determined based on PKs, safety, tolerability, and preliminary efficacy.

If a patient wishes to continuously receive study treatment on completion of Cycle 1, the patient can continue study treatment in 21-day Cycle 2 and subsequent cycles (same as Cycle 2, all of 21 days' duration), defined as administration of 3 times per week for 2 weeks followed by 1 week rest, at the discretion of the investigator.

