4.1.1 Dose Escalation

The DLT assessment period is 21 days starting from the first dose of FN-1501. The study will follow a standard 3+3 dose escalation scheme and a modified Fibonacci sequence until the MTD is reached. Increments of 33% in the dose of FN-1501 will be undertaken after reaching 30 mg/day. Because of the dosage form (10 mg/vial), each dose will be rounded to numbers such as 2.5, 5, 10, 15, 22.5 mg/day, etc. At least three (3) patients will be enrolled into each cohort.

Additional patient(s), up to a maximum of four (4) patients in total, may be enrolled in a cohort if more than three (3) have been screened and are eligible for the cohort.

The DLT assessment and dose-escalation scheme will follow the same principle as stipulated for a standard 3+3 dose escalation design. For example, one (1) to three (3) additional patients will be enrolled if a DLT is observed in one (1) of first three (3) patients. No additional patients are required if a DLT is observed in one (1) of six (6) patients.

The starting dose will be 2.5 mg/day administered on the assigned days. One possible dose escalation scheme is presented in Table 1. Other dose levels may be evaluated during the study, depending on emerging data.

August 21, 2019 Confidential 32 / 74

Table 1: Suggested Dose Escalation Scheme

Dose Level/Cohort	Dose (mg/d)	Increase (%)
1	2.5	100
2	5	100
3	10	50
4	15	50
5	22.5	33
6	30*	33
7	40*	33

The actual dose levels and dose regimens administered in each step will depend on the data available from the previous level, as determined by the Safety Monitoring Committee.

As currently planned, if none (0) of the patients in one cohort experience DLT during the DLT assessment period, the dose to be administered in the next cohort will be increased by up to 100% (up to the 10 mg/d dose), by up to 50% (for the 10 mg and 22.5 mg doses) and by 33% thereafter, as determined by the SMC formed by the medical monitor, investigator, and sponsor representative.

The dose intervals will follow standard 3+3 escalation rules starting with the treatment of 3 patients as follows:

- 1. If 0 of 3 patients experiences a DLT, dose escalation will proceed to the next higher dose level at which 3 patients (up to 4) will be enrolled.
- 2. If 1 of 3 patients experiences a DLT, 3 more patients will be enrolled at the same dose level.
- 3. Escalation will continue if 0 or 1 of 6 patients experiences a DLT.

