- 4. If 2 or more patients in any dose level experience a DLT, dosing will stop.

No additional patients will be treated at a given dose level if two (2) or more of the patients in the cohort develop a DLT during the DLT assessment period. In this instance, the MTD is considered to have been exceeded. If the MTD is exceeded, the next lower dose level is considered MTD. Depending on the decision of the SMC and on review of available data, an additional intermediate

August 21, 2019 Confidential 33 / 74

^{*} Increments of 33% in the dose of FN-1501 will be undertaken after reaching 30 mg/day until the MTD is reached.

dose level, between the MTD-exceeding dose level and the next lower dose level, may be explored. If an MTD is not identified due to paucity of DLTs, the RP2D will be determined based on PKs, safety, tolerability, and preliminary efficacy.

DLT Definition:

DLT is any AE not attributable to disease or disease-related processes that occur during the DLT assessment period. DLT is determined by investigators based on NCI-CTCAE Version 4.03:

Non-hematologic:

- Grade 3 or greater nausea, vomiting and diarrhea despite optimal supportive care
- Any other clinically relevant ≥ Grade 3 non-hematologic toxicity (excluding asymptomatic biochemical abnormalities that are not clinically significant and resolve to Grade 2 or less in <7 days)
- Persistent Grade 2 toxicity such as nausea, vomiting, or fatigue despite optimal standard medical therapy that, in the opinion of the investigator, prevents continuous dosing
- Any toxicity which in the judgment of the investigator or sponsor is dose limiting

Hematologic:

- Grade 4 neutropenia lasting > 7 days
- Grade 3 Febrile neutropenia (defined as absolute neutrophil count [ANC] < 1000/mm³ with a single temperature of 38.3°C or a sustained temperature of 38°C for > 1 hour)
- Grade 3 neutropenic infection
- Grade 3 thrombocytopenia with bleeding
- Grade 4 thrombocytopenia

For elevations in hepatic function enzymes, DLT is defined as follows:

- Grade 4 aspartate aminotransferase (AST) or alanine aminotransferase (ALT) increase
- AST or ALT > 5 × upper limit of normal (ULN) if accompanied by ≥ Grade 2 elevation in bilirubin
- AST or ALT > 5 × ULN lasting > 3 days in patients without liver metastases

August 21, 2019 Confidential 34 / 74

• AST or ALT > 5 × ULN lasting > 3 days if the baseline value was ≤ 3 × ULN in patients with liver metastases

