10.1 Sample Size Consideration

The number of dose levels examined and the emerging FN-1501 toxicities will determine the sample size. Based on toxicity data, 7 cohorts may be required to establish the dose of FN-1501 for phase 2 study. Assuming DLT starts to occur at the dose of 12.5 mg/day (4th cohort) and therefore, 6 patients will be enrolled into this and subsequent cohorts, it is estimated that approximately 33 patients will be required to establish the RP2D(s) of FN-1501.

The number of patients in each cohort has been based on a standard 3+3 with the desire to obtain adequate tolerability, safety, and PK data while exposing as few patients as possible to the study drug and procedures.

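### The MTD definition in the synopsis, 3.1 and 4.1 does not require that a higher dose was exceeded, so it can name an MTD where 4.1.1 assigns none

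*Protocol*

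**What the plan says.** Section 3.1 makes the MTD part of the primary endpoint: "The MTD of FN-1501 will be the highest dose under which one or no case of dose limiting toxicity (DLT) is observed". Section 4.1 repeats the rule ("The highest dose under which one or no case of DLT is observed will be considered as MTD"), and the synopsis carries it twice, under study design and under primary endpoints. No version mentions a higher level that was not tolerated.

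In the synopsis design text and in 4.1, the next sentence reads: "If DLT cannot be observed, RP2D will be determined based on safety, preliminary anti-tumor activities and PK data". Section 4.1 later adds: "If an MTD is not identified due to paucity of DLTs, the RP2D will be determined based on PKs, safety, tolerability, and preliminary efficacy". Section 4.1.1 repeats that sentence; 3.1 and the synopsis endpoint text do not.

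Section 4.1.1 works from the other direction. A level with two or more DLTs exceeds the MTD, and then: "If the MTD is exceeded, the next lower dose level is considered MTD". Lower counts are a reason to go up: none in three opens the next level, and for six patients "Escalation will continue if 0 or 1 of 6 patients experiences a DLT".

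**The concern.** Determining the MTD is a primary objective, and the protocol has two rules for it. By the short definition, every cleared level is the MTD until a higher one is cleared. By 4.1.1, clearing a level means only that escalation may go on, and an MTD emerges when a level above it fails.

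The sentence on an unidentified MTD makes sense only under the second rule. Under the short definition, any tested level with no more than one DLT supplies an MTD. One would be lacking only if no tested level qualified, which is the opposite of too few DLTs.

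At stake is what the report may conclude. From the same data it could present a dose as maximum tolerated although no intolerable dose was found, or say that the MTD was not reached.

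**Working it through.** **The plan's own figure.** Section 10.1 assumes seven cohorts, with six patients each from the fourth on: "6 patients will be enrolled into this and subsequent cohorts, it is estimated that approximately 33 patients will be required". Three cohorts of 3 plus four of 6 give 9 + 24 = 33, as stated. The figure does not depend on how the MTD is defined.

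**Both rules applied to the same outcomes.** Dose levels are from Table 1 (2.5, 5, 10, 15, 22.5, 30, 40 mg), and levels not mentioned are taken as 0/3. The short definition picks the highest tested level with at most one DLT. Section 4.1.1 picks the level below one with two or more DLTs.

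| Outcome | Short definition | 4.1.1 |
|---|---|---|
| 2/3 at 30 mg | 22.5 mg | 22.5 mg |
| 0/3 at every level to 40 mg, then stop | 40 mg | none assigned |
| 1/6 at 30 mg, 0/3 at 40 mg, then stop | 40 mg | none assigned |
| 1/6 at 40 mg, then stop | 40 mg | none assigned |
| 0/3 at 15 mg, then sponsor stops | 15 mg | none assigned |
| 2/3 at 2.5 mg | none | none |

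The rules part only where escalation ends with no level exceeded. Such an ending is possible: the SMC determines the dose levels (4.1), the sponsor may stop for administrative reasons (4.1.4), and the protocol provides for it ("If an MTD is not identified due to paucity of DLTs").

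**Reach of the nearest exception.** The sentence that follows the definition in 4.1 applies when no DLT is seen, and it fixes the basis for the RP2D. It does not say that the MTD is then undefined. The third and fourth rows each contain one DLT and fall outside it.

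**Illustration only.** Assume a DLT rate p per patient, cohorts of 3 then 6 (ignoring the optional fourth patient), and a stop after 40 mg. A level is not exceeded with probability (1−p)³ + 3p(1−p)²·(1−p)³. The chance that none of the seven levels is exceeded is the product of the seven terms; the zero-DLT part is the product of the (1−p)³ terms.

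- p = 5% throughout: one level 0.857 + 0.116 = 0.973; seven levels 0.828, of which 0.341 has no DLT and 0.488 at least one (rounded).
- p = 10% throughout: one level 0.729 + 0.177 = 0.906; seven levels 0.502, of which 0.109 has no DLT and 0.392 at least one (rounded).
- p rising 2, 3, 5, 10, 20, 30, 40%: seven levels 0.094, of which 0.020 has no DLT and 0.074 at least one.

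The spread from 9% to 83% shows that the answer is set by the assumed rates. None of these rates, nor the stop at 40 mg, is in the protocol.

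**The case against.** The best defence is that the passages can be read together. The short definition sits inside a 3+3 design that is to escalate until the MTD is found, so it can be taken as shorthand for where a completed 3+3 ends. The sentence on too few DLTs is then a specific exception to a general rule. For 4.1 this reading is reasonable. It does not help 3.1 or the synopsis endpoint text, which define the primary endpoint and carry no such exception.

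Second, 4.1.1 does not say in so many words that there is no MTD without an exceeded level. It says which level is the MTD if one is exceeded, and it leaves open how few DLTs count as too few. This stands: that 4.1.1 yields none is an inference from its silence. Four cohorts at 1/6 each would contain four DLTs, and nothing in the text settles whether that is too few.

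Third, a reader might infer that the sample-size plan itself leads to the conflict, since six-patient cohorts that still allow escalation would each end at 1/6, up to 40 mg. The protocol does not support that. Section 10.1 budgets patients; it neither predicts 1/6 in each cohort nor sets a stop after the seventh. After 1/6 at 40 mg the escalation rules and the footnote to Table 1 continue in 33% steps, and Table 1 is offered as one possible scheme. The conflict needs a stop that those rules do not prescribe.

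Finally, the consequence is limited, because the RP2D has its own stated basis whether or not an MTD is found.

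**Conclusion.** The point holds as an inconsistency in the definition of a primary endpoint. Followed literally, the synopsis, 3.1 and 4.1 report the highest dose tested as the MTD when no level had two or more DLTs; 4.1.1 gives no basis for naming one. This is a conflict between statements in the protocol, not detail that could be left to an analysis plan.

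Its reach is narrow. Once a level is exceeded and no intermediate dose is tested, both rules name the same dose. Cohort decisions, sample size and the RP2D basis do not change.

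The conclusion rests on a literal reading of the short definition and on escalation ending without an exceeded level. It does not rest on any DLT rate. A reader might take the probabilities above as showing that the conflict is likely, but the protocol gives neither DLT rates nor a fixed top dose, so its frequency cannot be derived. The wording should be corrected; the design need not be.

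**What to change.** In the synopsis (both places), 3.1 and 4.1, define the MTD as the highest level with no more than one DLT that lies below a level with two or more DLTs. State that if no level has two or more DLTs, the report will say that the MTD was not reached, give the highest dose evaluated, and choose the RP2D on the basis already stated. In the synopsis and 4.1, replace the condition that no DLT can be observed with the condition that no level has two or more DLTs, so that it also covers a study with isolated DLTs.

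The cost is wording in an amendment. Cohort rules, the 33 patients and the RP2D basis stay as they are. The downside is that the report may have to state that the MTD was not reached.
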